6. Prior to consumption of the Study Product, participants will be asked to completely void your bladder. And hydration status will be determined via urine specific gravity (USG) reporting <1.025. Urine passed after the ingestion of the study product will be collected in a plastic container; you will be asked to void their bladder and collect urine at the end of the test day. The volume produced will be recorded at the end of the study and aliquots will be frozen and stored for future analysis.
7. Participants will breathe into a commercially available handheld breath acetone analyzer according to the schedule in Figure 2. Participants will wear a fitted face mask attached to a metabolic cart for a 10-minute period every 60 minutes.
8. Participants will wear a Bluetooth heart rate monitor chest strap throughout the test day.
9. Participants will complete a Beverage Tolerability Questionnaire prior to Study Product consumption and at the end of the Test Day.
10. Participants will complete a 3-item satiety visual analogue scale prior to Study Product consumption and at the end of the Test Day.
11. Continuous Ketone Monitor will be applied at the start of Test Day 1. The sensor will be checked by the study team at each test day and will be removed and replaced by a fresh sensor at ~2- week intervals during the study. The sensor will be removed at the end of the final test day.

Screening Visit: Participants that meet the initial qualifying criteria will visit the study center for a screening meeting. The participant and a member of the research team will meet in a private office to discuss the informed consent form. The informed consent form will be provided to the participant for their review, the study will be described in full detail and any questions the interested participant has will be encouraged and responded to. If they choose to participate in the study, they will be asked to sign the consent form providing written consent. The participant will be informed that even though they signed the consent form, their participation in the study is dependent on anthropometric measures and diet and medical questionnaire answers to determine if they meet the study criteria.

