Statistical Plan. Statistical analysis of data will take place on completion of the study in collaboration with Buck Bioinformatics Core. Participant data will be included if they have completed at least 2 serving sizes of one exogenous ketone product AND the control Test Days (i.e., BHB- mono-ester 180 mg/kg, BHB mono-ester 360 mg/kg and Control). Any incomplete exogenous ketone compounds (i.e., participant completed C6 Di-ester 180 m/kg and AcAc ester at 360 mg/kg) will be excluded from the analysis. All decisions regarding exclusion from the analysis population will be documented prior to database lock. Missing data will not be imputed, and only observed data will be included in the statistical analysis.

Repeated measure group x time ANOVA (or a non-parametric alternative) will be performed following initial tests to ensure sphericity is not violated. We will compare data between control group vs. each individual exogenous ketone at both doses (i.e., control vs BHB-mono ester (180 mg/kg) vs BHB-mono-ester (360 mg/kg). We will also test for condition x time interactions. If significance is detected, post-hoc comparisons will be made using Tukey's HSD tests (or non-parametric alternative) to correct for multiple comparisons. Significance will be accepted at an alpha level of P < 0.05.

Other data processing:

- Area Under the Curve (AUC) will be calculated using the Trapezoid Rule.
- Maximal/minimal concentration data (C_{max} and C_{min}) and time of maximal/minimal concentration (T_{max} and T_{min}) will be extracted from the raw data.

- A composite tolerability score is calculated by adding the scores (0 -3, corresponding to none, mild, moderate, severe) of all ten listed symptoms.

STUDY MONITORING

Concomitant Medication/Supplements and Treatment

All concomitant medications/supplements used 1 months prior to Screening Visit and during the study will be reported to the study personnel for assessment and recorded in the participant's study documents.

Adverse Event Monitoring

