An AE is defined as any untoward medical occurrence in an investigation participant following written informed consent that does not necessarily have a causal relationship with the study product. An AE can be any unfavorable or unintended sign (including an abnormal finding), symptom, or disease temporally associated with the use of an investigational product, whether or not related to the investigational product. This includes any occurrence that is new in onset or aggravated in severity or frequency from the baseline condition, or abnormal results of diagnostic procedures (including laboratory test abnormalities).

Some side effects or GI symptoms could occur as an outcome of these dietary interventions; side effects listed in the beverage tolerability questions and reported will not be categorized as AEs but recorded as study outcomes. Side effects, outside of what is expected as a result of study product consumption, reported by participants and judged by the Investigators as medically relevant events and related to study product will be recorded as AEs.

Events should be considered AEs if they:

- Result in discontinuation from the study,
- Require treatment or any other therapeutic intervention,
- Require further diagnostic evaluation (excluding a repetition of the same procedure to confirm the abnormality),
- Are associated with clinical signs or symptoms judged by the Investigator to have a significant clinical impact.

Grading and Severity

The Investigator will evaluate all AEs with respect to their severity, and record the outcome and action taken on the AE study documents . AEs will be graded as:

Mild: Awareness of symptoms but easily tolerated

Moderate: Discomfort enough to interfere with but not prevent daily activity

Severe: Unable to perform usual activity

Relationship

The Investigator will also judge the likelihood that the AE was related to the study beverage and document this on the appropriate study documents as:

NOT RELATED	This category applies to those adverse experiences which, after careful consideration, are clearly and incontrovertibly due to extraneous causes (disease, environment, etc.).
UNLIKELY	In general, this category can be considered applicable to those experiences that after careful medical consideration at the time they are evaluated, are judged to be, unlikely related to the study beverage.

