All AEs (AE or SAE) will be recorded on the AE study documents. For participants who have an ongoing AE at their final study visit, follow-up information will be captured in the AE eCRF page which will be completed after 30 days.

Serious Adverse Event Follow-Up

For all ongoing SAEs occurring during the study, the Investigator must submit follow-up reports regarding the participant's subsequent course. All SAEs that are ongoing at the end of the study or upon discontinuation of the participant's participation must be followed until either:

- The event resolves, or
- The event/condition has stabilized (e.g., in the case of persistent impairment), or
- The event returns to baseline, if a baseline value is available, or
- The participant dies, or
- The event can be attributed to other than the study beverage, or to other than the study conduct.

CONDUCT OF THE STUDY

1. Ethics and Regulatory Considerations

This study will be conducted according to Good Clinical Practice Guidelines, the Declaration of Helsinki (2004) and United State Code of Federal Regulation Title 21. Signed written informed consent for participation in the study will be obtained from all participants before protocol-specific procedures are carried out. Participants will be

informed of their right to withdraw from the study at any time. Participants will be informed that their participation in the study is completely voluntary, personal information will be both deidentified to preserve anonymity.

2. Institutional Review Board

The Investigator will ensure that an appropriately constituted IRB, in compliance with the requirements of 21 CFR 56, reviews and approves the clinical study. Before the study is started, the Investigator will forward copies of the protocol and consent form for this study to the IRB for review and approval. IRB approval must refer to the study by exact protocol title and number, identify the documents reviewed, and state the date of review. The IRB must be informed of all subsequent protocol amendments. No alterations, modifications to IRB-approved documents, including the protocol, protocol summary, consent form, recruitment materials and questionnaires will be allowed. The IRB must also be informed of all SAEs and of unexpected AEs as outlined in the IRB's SOPs or reporting guidelines.

3. Informed Consent and Protected Health Information

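### The adverse-event section excludes every questionnaire-listed symptom from being an AE, then lists consequences that make an event an AE, and does not say which rule governs when both apply

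*Protocol*

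**What the plan says.** The Adverse Event Monitoring section of the protocol (under Study Monitoring) opens with a broad definition of an AE: any untoward occurrence after consent, whether or not the product caused it. Three statements follow.

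- **Exclusion.** "side effects listed in the beverage tolerability questions and reported will not be categorized as AEs but recorded as study outcomes".
- **Middle sentence.** "Side effects, outside of what is expected as a result of study product consumption" are recorded as AEs if participants report them and the investigators judge them medically relevant and related to the product.
- **Criteria list.** "Events should be considered AEs if they" meet any one of four conditions: they end participation, "Require treatment or any other therapeutic intervention", need further diagnostic work-up, or have a significant clinical impact in the investigator's judgement.

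The Beverage Tolerability Questionnaire section lists ten symptoms, among them vomiting, diarrhea, headache and dizziness. Each is scored 0 to 3, and the top grade means being unable to perform usual activity. On timing, "Participants will complete a Beverage Tolerability Questionnaire prior to Study Product consumption and at the end of the Test Day".

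For an AE, the Grading and Severity section states: "The Investigator will evaluate all AEs with respect to their severity, and record the outcome and action taken on the AE study documents". The Relationship section adds a relatedness category. The Recording of Adverse Events section adds follow-up: "For participants who have an ongoing AE at their final study visit, follow-up information will be captured in the AE eCRF page", completed after 30 days. The SAE definition describes an SAE as an AE with one of a set of serious outcomes.

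**The concern.** The exclusion is absolute for a listed symptom, whatever its severity or consequence. The criteria list covers events in general and makes no exception for listed symptoms. A listed symptom with one of the four consequences therefore falls under both statements, and they give opposite answers. Two staff members could code the same event differently, each with support in the text.

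At stake is the safety record. Vomiting or dizziness that needed treatment, made a man stop, or put him in hospital is what someone choosing between these products would want to see documented in full. If the exclusion is applied as written, such an event would not pass through relatedness assessment, follow-up or SAE reporting.

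**Working it through.** No arithmetic applies and the plan states no figure to reproduce. The check sets the statements side by side, runs one case through them, and lists what is kept under each reading.

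**Step 1: is there a linking word?** The exclusion carries no exception for severe or consequential symptoms. The criteria list carries no exception for listed symptoms. Nothing in the questionnaire, statistical, AE, SAE or withdrawal sections ranks one above the other.

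**Step 2: does the middle sentence settle it?** It sends to the AE record only side effects beyond what is expected. The exclusion sentence introduces the listed symptoms as effects that could occur with these products. If expectedness belongs to the symptom's name, vomiting stays excluded however bad it is. If it also depends on severity, treated vomiting may count as unexpected. The text does not say which, so the question stays open.

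**Step 3: a worked case.** A man vomits after the 360 mg/kg serving, needs treatment and withdraws.

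| Statement | Result |
|---|---|
| Exclusion | Vomiting is listed, so not an AE; study outcome only |
| Criteria list | AE on two criteria: treatment and discontinuation |

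**Step 4: what is recorded under each reading.**

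| Item | If an AE | If a study outcome only |
|---|---|---|
| Severity | Yes | Yes, on the questionnaire with the same three grade definitions |
| Outcome | Yes | Not required |
| Action taken | Yes | Not required as such; medication is logged |
| Relatedness | Yes | Not required |
| Follow-up if ongoing | Yes | Not required |

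The questionnaire supplies one of the five items, leaving 5 - 1 = 4 without a required entry. Two other records survive under either reading: concomitant medication (Concomitant Medication/Supplements and Treatment) and the reason for withdrawal (Withdrawal of Participants from the Study). Neither section asks for relatedness or follow-up.

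**Step 5: SAE status.** An SAE is defined as an AE with a serious outcome. If the exclusion prevails, a listed symptom that led to hospitalisation is not an AE and so does not formally meet the SAE definition.

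**Step 6: where the two statements do not collide.** A listed symptom that meets none of the four criteria is a study outcome under the exclusion, and the criteria list does not touch it. The ambiguity is confined to listed symptoms with one of the four consequences.

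**The case against.** The strongest reply is that the section has a natural reading without conflict. Events outside the exclusion already meet the broad opening definition, so the criteria list adds most if it brings excluded symptoms back in. It comes last, speaks of events in general and is specific about consequences. On that reading it is an escalation rule, and a hospitalised case would meet the treatment criterion and so be an AE. This is probably what was intended, so the defect is a missing connecting sentence rather than a proven contradiction of intent. But the escalation is not stated, and the middle sentence leaves it open.

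It is also fair that little is lost on severity, because the questionnaire uses the same grades as the AE form. The withdrawal section further asks for observations to be completed as fully as possible. Both points stand and limit the harm. They do not supply relatedness, follow-up or SAE status.

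A reader might infer something stronger: that the wording distorts the comparison of tolerability between products, because a man who stops early may also leave the analysis. The Statistical Plan does say "Participant data will be included if they have completed at least 2 serving sizes of one exogenous ketone product AND the control Test Days". But that rule works the same way whether or not the event is called an AE, and clarifying the AE wording would not alter it. It is a separate matter and gives no measure of this one.

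**Conclusion.** The point holds as a minor defect in safety-recording wording. The protocol fixes the AE definition itself, so this is not a detail that can wait for an analysis plan.

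The harm depends on staff applying the exclusion literally. In that case a listed symptom with a serious practical consequence lacks four of the five AE items and falls outside the SAE definition. If staff read the criteria list as an escalation rule, nothing is lost.

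How many events this would affect cannot be estimated. The documents give no symptom rates, and the 20% attrition allowance under Sample Size is not broken down by cause. A reader might be tempted to turn that allowance into a count of affected men, but the documents do not support it.

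The primary AUC outcome, the sample size and the composite tolerability score are the same under either reading.

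**What to change.** In Adverse Event Monitoring, directly after the exclusion sentence, add: *A listed symptom that meets any of the four criteria below, or any SAE criterion, is also recorded as an AE or SAE.*

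This states the escalation that was probably meant and closes the gap in the SAE definition. It needs no new visit, procedure or form. The one drawback is that a few symptoms will appear both as a study outcome and as an AE, so a safety report should say that the two counts overlap.

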NJ, USA) and ‘Avela’ (Genomatica, CA, USA), respectively. The AcAc Diester is commercially available (on Amazon <https://www.amazon.com/KetoLogic-Ketone-DiEster-Softgels>) and is currently being used in clinical studies of Angelman’s Disease²¹. We have been in communication with the companies that produce these exogenous ketones to ensure product availability and support for this work (see letters of support from BHB Therapeutics/Juvenescence and Disruptive Nutrition).

Quality Control: As only small amounts of product are needed for this study, and products are shelf stable, our aim is that all product inventory will be acquired at the start of the study to ensure the same product lots are used throughout. We plan to obtain Certificates of Analysis to confirm product exogenous ketone content.

Serving Size Rationale: Previous work has shown that lean body mass (LBM) is a major covariate in KE responsiveness⁹. Therefore, we will standardize exogenous ketone serving sizes to LBM (assessed using DXA) for all trials at 180 and 360 mg/kg LBM, which for a participant with 70 kg of lean mass corresponds to ~12.5 and 25 g, respectively. These serving sizes are representative of typical commercial serving sizes and are expected to elevate blood BHB in the range of 1.5 - 2 mM^{22,23}.

Blinding: It will not be possible to completely blind study participants or investigators due to visible differences between the C6 Ketone Di-ester and BHB-Mono-ester beverages and also the capsule delivery form for the AcAc Di-ester. However, study products will be coded (A, B, C, D and CON), and data analysts will remain blinded to the coding until analysis is complete.

Storage: The study products will be stored in a dry secure location at ambient temperature (15- 77°F) and are best served chilled. Study product supplies are to be used only in accordance with this protocol and under the supervision of the Investigator.

Table 1: Study product details

Study Active Ingredient	Serving Sizes	Form	Other product ingredients [ALLERGENS]	Example Commercial Product (Company)
BHB Mono-ester	180 mg/kg and 360 mg/kg	Ready to drink beverage	Water	DeltaG Tactical (TDeltaS Global, FL, USA)

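### The AE recording sentence adds a relatedness test that contradicts the protocol's own AE definition and causality scale, and can leave minor unrelated or procedure-caused effects unrecorded

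*Protocol*

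**What the plan says.** All of the AE text is in the protocol's Study Monitoring section.

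- **Definition (Adverse Event Monitoring).** An AE is any untoward medical occurrence after consent "that does not necessarily have a causal relationship with the study product". The next sentence repeats the point for signs, symptoms and disease, "whether or not related to the investigational product". Laboratory abnormalities are included by name.
- **Questionnaire symptoms (same section).** Here "side effects listed in the beverage tolerability questions and reported will not be categorized as AEs but recorded as study outcomes".
- **Recording sentence (same section).** Side effects beyond those expected from the product, if reported by participants and "judged by the Investigators as medically relevant events and related to study product will be recorded as AEs".
- **Four criteria (same section).** Under the lead-in "Events should be considered AEs if they", the protocol lists discontinuation, a need for treatment, a need for further diagnostic work, and significant clinical impact. None of the four mentions relatedness.
- **Causality scale (Relationship).** Each AE is graded as NOT RELATED, UNLIKELY, POSSIBLY, PROBABLY or DEFINITELY.
- **Recording of Adverse Events.** Every AE goes onto the AE study documents.
- **Blinding (Study Products).** "It will not be possible to completely blind study participants or investigators". The design is open label.

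**The concern.** A causality scale only makes sense if events are written down first and attributed second. The recording sentence appears to reverse that order for unexpected, participant-reported effects: it names relatedness as part of what gets an event recorded. An event left out for that reason never reaches the scale, and nobody can reassess its cause later from the AE documents. The person making the judgement will often know which product was taken that day.

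What is at stake is whether the safety record is complete for small events. Procedures are frequent in this trial, so minor effects with a cause other than the product are foreseeable. The section on the Institutional Review Board also provides for reporting of unexpected AEs, and an unexpected event that was never recorded cannot be considered for that step.

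**Working it through.** No calculation decides this point, and the protocol states no figure to reproduce. The check is to run typical events through each rule.

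**1. Definition against recording sentence.** The definition sets causality aside twice. The recording sentence asks for it. If the sentence is not a filter it does nothing, because the definition already makes every such effect an AE. It also directly follows a carve-out of what will not count as an AE, so site staff would naturally read it as a second limit.

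**2. Recording sentence against causality scale.** An effect admitted because it was judged related cannot then be graded NOT RELATED, and hardly UNLIKELY. For effects handled by this sentence alone, the two lowest of the five grades would have no entries.

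**3. What each rule does with an event judged unrelated to product:**

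| Event | Definition | Recording sentence | Four criteria | Result |
|---|---|---|---|---|
| Mild cannula- or sensor-site reaction reported by the participant; no treatment, work-up, withdrawal or significant impact | AE | Not admitted | None met | Depends on which text the site follows |
| The same reaction, treated | AE | Not admitted | Met | AE, can be graded NOT RELATED |
| Intercurrent illness leading to withdrawal | AE | Not admitted | Met | AE, can be graded NOT RELATED |
| Abnormal value on the handheld blood analyzer | AE, named in the definition | Does not apply: not reported by the participant | Depends on follow-up | AE by definition |

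Only the first row is exposed. Questionnaire symptoms are dealt with by their own sentence and are not in question here.

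**4. Does the general recording rule close the gap?** No. It covers all AEs, so it depends on what counts as an AE, which is the point left unclear.

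**5. Opportunity for such events.** The protocol gives one cannulation per Test Day, nine Test Days, seven venous samples per day each with a finger-stick sample, and three ketone sensors per participant. With 15 participants completing every day:

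- cannulations: 15 × 9 = 135
- venous samples per participant: 7 × 9 = 63, with as many finger sticks
- sensors: 15 × 3 = 45

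These are numbers of procedures, not of events. They show that minor procedure effects are foreseeable, not how many would be lost.

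**The case against.** The strongest reply is that the sentence states when an effect will be recorded and does not contain the word only. Taken literally it is a sufficient condition. The definition and the rule that all AEs are recorded still stand, so a careful site would record unrelated events anyway. The sentence also speaks of side effects, and a cannula bruise might be thought to lie outside that term altogether. This stands to the extent that non-recording is an inference and not a stated rule. It does not remove the conflict. On the literal reading the sentence is redundant. By asking whether a side effect is related, it also uses the term broadly enough to include unrelated ones. Staff are left with three tests for what to write down.

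The second reply is that the four criteria need no relatedness and catch everything of consequence. That is largely right and limits the finding: treated or investigated procedure events are AEs, and a serious event would almost always meet a criterion. What remains is the minor event that meets none of the four.

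Two stronger readings are tempting and should be resisted. A reader might infer that the rule hides all unrelated and procedure-caused events, laboratory values included; the four criteria and the sentence's restriction to participant reports rule that out. A reader might also infer that it biases a product-versus-control safety comparison. No AE comparison appears among the outcomes or in the Statistical Plan. The planned tolerability comparison uses the questionnaire, which has no causality filter, and acid-base measures are collected whatever their AE status. Any ratio of recorded AE rates between product and control days would only restate the recording probabilities assumed for it.

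**Conclusion.** The concern holds in limited form. The recording sentence is wrong as written: its relatedness condition conflicts with the AE definition and with the lower end of the causality scale in the same part of the protocol. If sites read it as a filter, which is the reading that gives it any function, minor participant-reported effects judged unrelated or procedure-caused, and meeting none of the four criteria, may go unrecorded at the discretion of an investigator who is not fully blinded.

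The consequence is an incomplete safety record for minor events. The primary and secondary outcome analyses are not affected. The effect on serious events is small. No count of lost events can be given, because the protocol supplies neither an event rate nor a rate at which events would be judged unrelated. The conclusion rests on the filter reading. On the lenient reading the text is still ambiguous and still needs reconciling.

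**What to change.** - Delete the closing relatedness phrase from the recording sentence.
- State that events outside the tolerability questionnaire are recorded according to the AE definition, and that relationship is judged afterwards on the existing five-level scale.
- Reconcile the four-item list with the definition by saying what role it has: whether it marks the more consequential AEs or limits what counts as one. The medical-relevance condition in the recording sentence should be made consistent at the same time. The contradiction over causality does not by itself require removing that condition or demoting the list, so those remain the sponsor's choice, provided that the texts agree.

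The cost is one phrase deleted, a clarifying sentence or two, and probably a few more AE entries in a 15-person study. The change concerns documentation only.
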